9.4. Causality of Adverse Event

9.4.1. Relation to investigational product

The Investigator will assess the causality/relationship between the investigational product and the AE and record that assessment in the source documents and in the e-CRF. The most likely cause of an AE/SAE (for example disease under treatment, concomitant disease, concomitant medication, other) will be indicated in the e-CRF.

In the absence of a definite causal relationship, any adverse event that is considered to have a reasonable causal relationship with the investigational product should be classified as "probably related."

The causal relationship of the AE to investigational product will be described in terms of:

1. Related. The AE:

- 1. Follows a clear temporal sequence from administration of the investigational product.
- 2. Has no other possible explanations, such as the subject's clinical state, environmental or toxic factors or other therapies administrated to the subject.
- 3. Disappears or decreases on cessation or reduction in dose of the investigational product.
- 4. Follows a clear pattern of response to the investigational product.
- 5. Reappears or worsens upon re-challenge.

2. Probable. The AE:

- 1. Follows a reasonable temporal sequence from administration of the investigational product.
- 2. Could not be reasonably explained by the subject's clinical state, environmental or toxic factors or other therapies administrated to the subject.
- 3. Disappears or decreases on cessation or dose reduction of the investigational product.
- 4. Follows a known pattern of response to the investigational product.
- 5. Reappears or worsens upon re-challenge.

3. Possible. The AE:

- 1. Follows a reasonable temporal sequence from administration of the investigational product.
- 2. Could be reasonably explained by the subject's clinical state, environmental or toxic factors or other therapies administrated to the subject.
- 3. Follows a known pattern of response to the investigational product.

4. Unlikely. The AE:

- 1. Does not follow a reasonable temporal sequence from administration of the investigational product.
- 2. Could be reasonably explained by the subject's clinical state, environmental or toxic factors or other therapies administrated to the subject.
- 3. Does not follow a known pattern of response to the investigational product.
- 4. Does not reappear or worsen upon re-challenge.

5. Not related.

- The AE does not meet the above criteria.
- 2. There is sufficient information that the etiology of the AE is not related to the investigational product.

9.5. Recording Adverse Events occurring after the end of the study

Adverse events occurring after the end of the study should be reported to the Sponsor by the Investigator if the Investigator considers that there is a causal relationship with the investigational product.

9.6. Adverse Event Reporting

At each clinical evaluation, the Investigator will determine whether any AEs have occurred. AEs will be recorded in the AE page of the e-CRF as well as in the source documents.

Coding of AEs will be performed using MedDRA (https://www.meddra.org/). All AE reports in the e-CRF should contain the following information of the event: date of onset, severity, relationship to investigational product, outcome at Day 30, and whether the event is classified as serious or not.

9.6.1. Serious Adverse Event Reporting

SAEs that are unexpected and either definitively or probably related to the investigational products (Suspected Unexpected Serious Adverse Reactions – SUSARs) must be reported to the sponsor. SAEs that are expected and either definitively or probably related to the investigational product and non-CCP related SAEs that meet reporting criteria (unexpected in the context of COVID-19, critical illness, or a baseline medical condition; or not already reported as a study outcome) must also be reported to the sponsor.

In the event of a SAE, the Investigator must:

- 1. Enter all relevant information in the AE page of the eCRF.
- 2. Inform the Sponsor of the SAE via email or telephone within 96 hours of becoming aware of the SAE (or within 24 hours if SAE is unexpected and related to investigational product, see section 9.8).
- 3. Complete the SAE reporting form in the EDC.

The minimum information required for an initial report is:

- 1- Name of person sending the report (that is name and address of Investigator);
- 2- Confirmation that the patient was in the active treatment arm;
- 3- Subject identification (screening number, NOT the subject's name);
- 4- Protocol number;
- 5- Description of the SAE including a comprehensive verbatim term;

- 6- Event onset date;
- 7- Causality assessment, if possible.

However, as far as possible, all points in the SAE pages in the e-CRF and on the SAE Report Form should be covered in the initial report.

SAE update reports should be submitted to the Sponsor when additional relevant information becomes available.

Suspected unexpected serious adverse reactions (SUSARS) will be submitted by the Sponsor or its representative to the Regulatory Authorities according to local guidelines.

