7. DURATION OF FOLLOW-UP

Subjects will be followed daily until hospital discharge or death. Patients discharged from hospital before Day 30 will be contacted by telephone on Day 30 ± 3 days to ascertain any AEs, vital status (dead/ alive), hospital readmission and need for mechanical ventilation after discharge. Patients with a prolonged hospital admission will be censored for the outcome of in-hospital death at Day 90.

For patients who are pregnant or who become aware that they are pregnant between the period of randomization and Day 30, we will record their expected date of delivery and we will contact the patient after delivery to obtain information regarding any maternal or fetal adverse outcomes.

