9. SAFETY VARIABLES

9.1. Adverse Event

An AE is any untoward medical occurrence that occurs in a patient or clinical investigation subject administered a pharmaceutical product, and which does not necessarily have a causal relationship with the treatment assignment. An AE can therefore be any unfavorable and unintended sign (including abnormal laboratory finding), symptom, or disease temporally associated with the use of an investigational product, whether or not considered related to the product.

Because this is a trial focusing on a critically ill population where serious adverse events and death are expected to occur frequently, AE reporting will follow recommendations set out for trials in this population by Cook and colleagues⁵⁰. During this trial, investigators will need to document all AEs that are definitely or probably related to the intervention (defined in 9.4.1), and events that are grade 3 or higher for all other AEs.

These will be documented on the paper CRF and in the electronic CRF (e-CRF) with the maintenance of all source documentation in the patient research file. Concomitant illnesses, which existed before entry into the study, will not be considered AEs unless they unexpectedly worsen during the treatment period. AEs must be documented regardless of the source of identification (for example physical examination, laboratory assessment, reported by subject).

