9.8. Reporting and Entry Timelines

Study investigators will report SAEs to the sponsor within the following timelines:

- All serious and unexpected events deemed to be related to investigational product (suspected unexpected serious adverse reaction (SUSAR)) will be recorded and reported to the sponsor within 24 hours of site awareness.
- All other SAEs will be reported to the sponsor within 96 hours of site awareness.

Adverse event information will be entered into the CRF in a timely manner and **no later than 7** days from the time the investigator becomes aware of the event.

Serious adverse event information will be entered into the CRF in a timely manner/within 96 hours from the time the investigator becomes aware of the event (or 24h for SUSARs).

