9.10.1. Pregnancy

The Sponsor has a responsibility to monitor the outcome of pregnancies where there has been maternal exposure to the investigational product. Pregnancy alone is not regarded as a contraindication to participation in the trial or as an AE unless there is a suspicion that the investigational product may have interfered with the effectiveness of a contraceptive medication. Elective abortions without complications should not be handled as AEs, unless they were therapeutic abortions (see below). Hospitalization for normal delivery of a healthy newborn will not be considered a SAE.

All pregnancies occurring in the CCP group must be reported by the Investigator to Sponsor on a separate CRF within 24 hours after becoming aware of the pregnancy. The Investigator must follow up and document the course and the outcome of all pregnancies even if the subject was discontinued from the study or if the study has finished. All outcomes of pregnancy must be reported by the Investigator to the Sponsor on a specific pregnancy CRF within 96 hours after she/he has gained knowledge of the normal delivery or elective abortion.

Any SAE related to investigational product that occurs during pregnancy (including SAEs occurring after last administration of investigational product) must be recorded in the SAE pages in the CRF (for example serious maternal complications, spontaneous or therapeutic abortion, ectopic

pregnancy, stillbirth, neonatal death, congenital anomaly, or birth defect) and reported within 96 hours in accordance with the procedure for reporting SAEs.

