11.8. Protocol Approval and Amendment

Before the start of the study, the study protocol and/or other relevant documents will be reviewed and approved by the REB/IRB/IEC/Regulatory Authorities, in accordance with local legal requirements. The Sponsor must ensure that all ethical and legal requirements have been met before the first subject is enrolled in the study.

This protocol is to be followed exactly. Any change to the protocol must be handled as a protocol amendment. Any potential amendment must be approved by the Sponsor. A written amendment must be submitted to the appropriate Regulatory Authorities and to the REB/IRB/IECs assuming this responsibility. The Investigator must await REB/IRB/IEC approval of protocol amendments before implementing the changes, except where necessary to eliminate apparent immediate hazard to subjects.

All substantial amendments to the protocol must be approved in writing by both the appropriate Regulatory Authorities and the REB/IRB/IEC, except for administrative amendments, which require notification or protocol addendums but not written approval or modifications that are subject to the Health Canada interim order for clinical trials on COVID-19 issued June 2nd 2020. Once approved, the protocol amendment will be distributed to all recipients of the original protocol, with instructions to append the amendment to the protocol. If, in the judgment of the local REB/IRB/IEC, the Investigator and/or Sponsor, the protocol amendment alters the study design, procedures and/or increases the potential risk to the subject, the currently approved written ICF will require modifications.

The modified ICF must also be reviewed and approved by the Sponsor, appropriate Regulatory Authorities, and the REB/IRB/IEC. In such cases, repeat informed consent must be obtained from the enrolled subjects or parents/guardians before participation continues.

11.9. **Duration of the Study**

For an individual subject, study ends for a subject 89 days after randomization (except for pregnant women on the CCP arm, which should be followed until pregnancy outcome is known). The overall study will end when the last randomized subject has reached the Day 90 time point. The inclusion of new participants will be determined based on new data and clinical needs according to the evolution of the pandemic. The planned study duration is 1 year.

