Serious adverse events (unexpected and meeting criteria for expedited reporting to the sponsor, Hamilton Health Sciences) will be analyzed as summarized below. TRALI and TACO adverse events, while not technically considered SAEs, require expedited reporting to the sponsor; hence they will be also be included.

The number and proportion of individuals experiencing a serious adverse event will be reported by event type, overall and by treatment arm. A second analysis will be by event which will accommodate the possibilities of multiple events per individual.

In the interim and final analyses, the relative risk reduction for death (CCP versus standard of care) will be computed along with a 95% confidence interval. The relative risk reduction (CCP versus standard of care) will also be computed for SAEs (regardless of outcome) along with a 95% confidence interval.

The cumulative incidence of serious adverse event will also be plotted by treatment group.

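### The minimum initial SAE report in Protocol 9.6.1 cannot be completed for a control patient, and the protocol disagrees with itself on following control-arm pregnancies

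*Protocol*

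**What the plan says.** **SAE reporting.** After listing the product-related SAEs that go to the sponsor, Protocol 9.6.1 adds "non-CCP related SAEs that meet reporting criteria". Protocol 9.8 sets the clock for these: "All other SAEs will be reported to the sponsor within 96 hours of site awareness". Neither sentence is limited by arm. Protocol 9.6.1 then lists the minimum information for an initial report, and item 2 of that list is "Confirmation that the patient was in the active treatment arm".

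**SAE analysis.** SAP 4.3.13 (Grade 3, 4 and 5 serious adverse events at Day 30) describes the SAEs to be analysed as unexpected events that qualify for expedited reporting to the sponsor, and adds TRALI and TACO. It states: "The number and proportion of individuals experiencing a serious adverse event will be reported by event type, overall and by treatment arm". It also plans a relative risk reduction for SAEs, CCP against standard of care, with a 95% confidence interval, and a cumulative incidence plot by arm.

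**Pregnancy.** Protocol Section 7 covers patients who are pregnant, or learn that they are, between randomization and Day 30. The expected delivery date is recorded and "we will contact the patient after delivery to obtain information regarding any maternal or fetal adverse outcomes". No arm is named. Protocol 9.10.1 says "All pregnancies occurring in the CCP group must be reported by the Investigator to Sponsor", within 24 hours. Protocol 11.9 ends an individual's study 89 days after randomization, "except for pregnant women on the CCP arm, which should be followed until pregnancy outcome is known".

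**The concern.** Sites know the allocation. When a control patient has a reportable SAE, the instructions tell the site to report it and then ask for a confirmation that would be false. A site could reasonably take this to mean that the form is not meant for control patients. If some sites did so, fewer control events would reach the channel that SAP 4.3.13 uses for its by-arm comparison, and the imbalance could be read as harm from CCP. Safety tabulations that include SAEs also go monthly, unblinded, to the IDSMC (SAP 4.5 and 4.11), and Protocol 10.1 leaves stopping for harm to that committee's judgement.

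On pregnancy, the three passages give a site no single answer on whether to follow a pregnant control patient to the outcome. Control outcomes are what maternal and fetal events after CCP would be read against.

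**Working it through.** The documents state no SAE rate, no reporting completeness and no expected number of pregnancies, so there is no plan figure to reproduce. The check is a comparison of passages.

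**1. Which rules are limited to CCP?**

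| Rule | Place | Arm limit |
|---|---|---|
| Documenting "events that are grade 3 or higher for all other AEs" | Protocol 9.1 | None |
| Adverse Event Review | Protocol 8.3, schedule | None; the CCP-only footnote is attached to CCP administration |
| Collection starts at randomization, ends at Day 30 | Protocol 9.7 | None |
| Reporting of SAEs unrelated to CCP | Protocol 9.6.1 | None |
| 96 hours for all SAEs other than SUSARs | Protocol 9.8 | None |
| Grade 3 to 5 events on the eCRF | SAP 2.3.1 | None |
| Safety sample is all randomized patients | SAP 3.3 | None |
| Minimum initial SAE report, item 2 | Protocol 9.6.1 | CCP only |
| Pregnancy report to the sponsor | Protocol 9.10.1 | CCP only |
| Pregnancy follow-up beyond the individual end of study | Protocol 11.9 | CCP only |
| Contact after delivery | Protocol 7 | None |

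**2. Item 2 against the duty in its own section.** A control patient's SAE falls under the duty to report SAEs unrelated to CCP. Item 2 is listed as required information and is not worded as a request to state the arm. For that patient it can be left blank or answered falsely, but not met. The two parts of 9.6.1 contradict each other.

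**3. Link to the analysis.** SAP 4.3.13 ties entry into the SAE analysis to sponsor-reporting criteria. Having grade 3 to 5 events on the eCRF in both arms therefore does not by itself guarantee that the SAE comparison is symmetric.

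**4. Pregnancy timeline.** Randomization is Day 1 (SAP 2.1), so 89 days later is Day 90. For a control patient who delivers by Day 90, Section 7 and 11.9 do not collide. For one who delivers later, Section 7 requires contact after delivery, while 11.9 says her study has ended. In 9.10.1 the first reporting sentence names the CCP group, and the next two speak of all pregnancies and all outcomes without repeating or lifting that limit.

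**5. Size.** If true SAE risk were equal and control events were captured with completeness *c* relative to CCP, the apparent relative risk would be 1/*c*: 1/0.95 = 1.05, 1/0.90 = 1.11, 1/0.80 = 1.25, 1/0.70 = 1.43. These values of *c* are assumptions. Nothing in the documents favours any of them over *c* = 1, at which the ratio is 1.00. The calculation shows only how a difference in capture would carry through.

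**The case against.** A reader might infer that the SAE rules are written for the CCP arm only. They are not: the table shows the collection rules applying to both arms.

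A reader might go further and say that the SAE relative risk is pushed against CCP. The strongest case against that runs as follows:

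- Item 2 is one line in a content list and does not define which events are reportable.
- Nothing says that a report lacking it is rejected.
- The SAE form itself is not in the documents.
- Protocol 9.6.1 separately requires an entry on the eCRF adverse event page, and 9.6 has each entry flag seriousness.
- Remote monitoring compares eCRF entries with medical records (Protocol 11.4.1).
- Much by-arm harm data bypasses the list. Grade 3 to 5 adverse events are analysed separately by arm, and death, intubation, ECMO, renal replacement and myocarditis are outcomes for everyone.

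All of this stands. It reduces the issue to a risk of under-reporting but does not remove the contradiction.

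A third tempting reading takes the SAP's word *expedited* to mean the 24-hour SUSAR rule, which needs relation to the product and would all but exclude control patients. The SAP does not define the term, and the 96-hour rule would admit control events, so this cannot be concluded.

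On pregnancy, a reader might infer that CCP pregnancies have no concurrent comparator. Section 7 provides one. The 24-hour report in 9.10.1 also has its own rationale, maternal exposure to the product, and can coexist with Section 7. Pregnancy alone is generally not an adverse event under 9.10.1, and the SAP plans no pregnancy comparison, so the CCP-only pregnancy report does not itself enter the SAE relative risk.

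**Conclusion.** The point holds as two defects of wording. First, item 2 of the minimum SAE report cannot be met for a control patient and contradicts the reporting duty in its own section. Because sites are unblinded and SAP 4.3.13 relies on sponsor-reporting criteria, this creates a risk of lower control-arm reporting. That judgement assumes that some sites might take item 2 literally; the documents neither show nor exclude this. The size of the risk is unknown, and the 1/*c* values are not evidence of severity. Second, Section 7 conflicts with 11.9 for control patients who deliver after Day 90, and 9.10.1 provides a sponsor report only for the CCP group. The number affected is not stated and is likely small. Both are worth correcting because they affect what is collected.

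**What to change.** 1. In Protocol 9.6.1, replace item 2 with: *Randomized arm, and whether and when CCP was transfused*. Check that the SAE form matches.
2. Reconcile Protocol Section 7, 9.10.1 and 11.9 so that pregnancy outcomes are collected in both arms, as Section 7 states. In 11.9, the exception to the 89-day end of study should cover pregnant patients in either arm. In 9.10.1, state that course and outcome are documented for both arms. The 24-hour sponsor report may stay limited to CCP-exposed patients.

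The cost is a protocol wording change, any matching change to the SAE form, and contact after delivery for the few pregnant control patients, which Section 7 already promises. Keeping the 24-hour report limited to CCP-exposed patients avoids extending that duty to unexposed controls.

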9.6.2. Sponsor Reporting of SUSARs: Notifying Health Canada

The regulatory sponsor (or its delegate) is responsible for reporting SUSARs to regulatory authorities in accordance with local expedited reporting requirements and timelines. In addition, the Sponsor will complete the Adverse Drug Reaction Expedited Reporting Summary Form and submit this form to the appropriate Health Canada directorate.

Any unexpected fatal or life-threatening suspected adverse reaction will be reported to the regulatory authority as soon as possible, but in no case later than 7 calendar days after the sponsor's initial receipt of the information. If the event is not fatal or life-threatening, the safety report will be submitted within 15 calendar days after the sponsor determines that the information qualifies for reporting. Relevant follow up information to safety report will be submitted as soon as the information is available. Upon request from regulatory authority, the sponsor will submit any additional data or information that the agency deems necessary, as soon as possible, but in no case later than 15 calendar days after receiving the request.

9.6.3. Reporting of Serious Adverse Events to the FDA

The U.S. site regulatory sponsor/sponsor representative is responsible for notifying the FDA of any suspected adverse reaction to study treatment that is both serious and unexpected to the FDA. The event will be filed on the FDA Form 3500A and submitted as soon as possible but no later than 7 calendar days after the initial receipt of the information to CBER.

All transfusion-related fatalities must be reported as soon as possible to Food and Drug Administration (FDA), Center for Biologics Evaluation and Research (CBER), Office of Compliance and Biologics Quality (OCBQ) after confirming a complication of blood collection or transfusion to be fatal. The collecting facility is to report donor fatalities, and the compatibility testing facility is to report recipient fatalities. The regulation also requires the reporting facility to submit a report of the investigation within 7 days after the fatality.

9.6.4. **Reporting of Serious Adverse Events to** Agência Nacional de Vigilância Sanitária (ANVISA-Brazil)

The regulatory sponsor/sponsor representative (or its delegate) is responsible for reporting Adverse Events to national regulatory authorities (ANVISA) in accordance with local expedited reporting requirements and timelines. Relevant follow up information to safety report will be submitted as soon as the information is available. Upon request from regulatory authority, the sponsor will submit any additional data or information that the agency deems necessary, as soon as possible, but in no case later than 15 calendar days after receiving the request.

The sponsor will also notify the local IRB and CONEP, within a maximum period of 24 hours, of any serious adverse event, suspected of having been caused by the proposed treatment (including death).

9.6.5. Reporting of Serious Adverse Events to the Meir Medical Centre Ethics Committee and Israeli Ministry of Health

The Israeli site regulatory sponsor/sponsor representative is responsible for notifying the Meir Medical Center Ethics Committee and to the Israeli Ministry of Health when considered necessary by the former body, of any suspected adverse reaction to study treatment that is both serious and unexpected. The event will be reported as soon as possible but no later than 7 calendar days after the initial receipt of the information.

